6.6.6.5 Cardiac Findings

AZD0466 should be withheld if any of the following occur at any time during study intervention:

- Symptomatic tachycardia
- Symptomatic hypotension
- QTcF shortening by 60 milliseconds compared to baseline, or interval value < 340 milliseconds, confirmed on at least 2 separate ECGs recorded 5 minutes apart
- QTcF prolongation of > 500 milliseconds or QTcF prolongation from baseline by 60 milliseconds, confirmed on at least 2 separate ECGs recorded 5 minutes apart
- Any other cardiac findings of CTCAE Grade ≥ 2 or considered by the Investigator to be clinically significant.
- AZD0466 should be permanently discontinued if a CTCAE Grade ≥ 3 cardiac AE of any duration occurs during study intervention, if considered by the Investigator to be related to study intervention.

Further investigation of the cardiac findings should be considered, including referral to a cardiac specialist. Patients should be monitored closely. AZD0466 may be restarted after resolution of cardiac findings to the patient's baseline at the discretion of the Investigator and after discussion with the Study Physician.

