8.3.4 Adverse Events Based on Signs and Symptoms

All AEs spontaneously reported by the patient or reported in response to the open question from the study site staff: ‘Have you had any health problems since the previous visit/you were last asked?’, or revealed by observation will be collected and recorded in the eCRF. When collecting AEs, the recording of diagnoses is preferred (when possible) to recording a list of signs and symptoms. However, if a diagnosis is known and there are other signs or symptoms that are not generally part of the diagnosis, the diagnosis and each sign or symptom will be recorded separately.

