10.6.6.3 Definition of DLT

A DLT will be defined as the occurrence of any of the following during the 28-day DLT evaluation period in Cycle 1, unless unequivocally due to underlying malignancy or an extraneous cause:

- Haematologic toxicity:
 - CTCAE Grade 3 thrombocytopenia of any duration, associated with Grade ≥ 2 bleeding or requiring platelet transfusion
 - CTCAE Grade 4 thrombocytopenia lasting > 7 days
 - CTCAE Grade 4 anaemia
 - CTCAE Grade 4 neutropenia lasting > 7 days
 - CTCAE Grade ≥ 3 febrile neutropenia (ANC $< 1.0 \times 10^9/L$, fever $> 100.9^{\circ}\text{F}$ [or $> 38.3^{\circ}\text{C}$]) of any duration despite supportive care

- Non-haematologic toxicity:
 - Any CTCAE Grade 3 non-haematologic toxicity lasting > 7 days OR any CTCAE Grade 4 non-haematologic toxicity, with the exception of:
 - CTCAE Grade 4 nausea, vomiting, or diarrhoea lasting < 72 hours in the absence of maximum supportive therapy.
 - Elevation in serum amylase and/or lipase without clinical or radiographic evidence of pancreatitis.
 - CTCAE Grade 3 fatigue, asthenia, fever, anorexia, or constipation.
 - Any other cardiac findings of CTCAE Grade ≥ 2 if considered by the Investigator to be clinically significant. AZD0466 should be permanently discontinued if a CTCAE Grade ≥ 3 cardiac AE of any duration occurs at any time during study intervention, if considered by the Investigator to be related to study intervention.
 - Liver function test abnormalities meeting Hy's Law or potential Hy's Law criteria.
 - Cairo-Bishop Grade ≥ 3 clinical TLS ([Appendix G](#)) that occurs despite protocol-recommended management.
 - Cairo-Bishop Grade ≥ 3 laboratory TLS ([Appendix G](#)) with metabolic abnormalities that do not resolve within 5 days despite protocol-recommended management.
- Any other toxicity that is greater than that at baseline, is clinically significant and/or unacceptable, does not respond to supportive care, results in a disruption of dosing schedule of more than 21 days or is judged to be a DLT by the SRC (toxicity that is clearly and directly related to the primary disease or to another aetiology is excluded from this definition).
- Any CTCAE Grade 5 AEs (please also see Section [4.5](#), study-wide stopping criteria)

Dose-limiting toxicities will not include the following:

- Transient isolated laboratory abnormalities which are not considered clinically significant and resolve to baseline within 72 hours without any intervention.

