	High	Intermediate	Low
Anti-hyperuricemics	Allopurinol 100 to 300 mg every 8 hours Early consideration of rasburicase ^a as an alternative, based on baseline uric acid and tumour burden		Allopurinol 100 to 300 mg every 8 hours
Criteria for use of rasburicase			
Serum uric acid at baseline	> 475.8 µmol/L ^b + 1 risk factor ≤ 475.8 µmol/L ^b + 2 risk factors	> 475.8 µmol/L ^b + 2 risk factors ≤ 475.8 µmol/L ^b + 3 risk factors	NA
Risk factors	Serum creatinine > 1.3 mg/dL (> 88.4 µmol/L) WBC > 50 × 10 ⁹ /L LDH > 2 × ULN		NA

^a Rasburicase is contraindicated in patients with glucose-6 phosphate dehydrogenase deficiency, known hypersensitivity to rasburicase, haemolytic anaemia or methemoglobinemia

^b Uric acid cutoff may be adjusted according to local guidance.

Recommended prophylaxis adapted from MD Anderson Cancer Center guidance ([Coiffier et al 2008](#)) and Cairo and Bishop ([Cairo and Bishop 2004](#)).

IV = intravenous; LDH = lactate dehydrogenase; TLS = tumour lysis syndrome; WBC = white blood cell.

F 1.2 AZD0466 Dose Modifications for Tumour Lysis Syndrome

AZD0466 dose modifications for TLS are summarised in [Table F29](#).

Table F29 AZD0466 Dose Modifications for Tumour Lysis Syndrome

Abnormality	Action with AZD0466
Laboratory findings (serum)	
Uric acid ≥ 475.8 µmol/L	
 Initiate supportive therapy as per standard clinical practice, additional guidance provided in Table F30.
Potassium ≥ 6.0 mmol/L	
Phosphate ≥ 1.6 mmol/L (5.0 mg/dL) with ≥ 0.16 mmol/L (0.5 mg/dL) increase ^a	
 Delay AZD0466 for up to 7 days (if finding present before administration of AZD0466) If resolution to within specified threshold in ≤ 7 days, restart at the same dose level If resolution after 7 days restart AZD0466 at one lower dose
Corrected calcium < 1.75 mmol/L	
Creatinine increase by > 26.5 µmol/L from baseline (creatinine > 1.5 × ULN if no baseline)	
All laboratory abnormalities must resolve to within specified threshold before AZD0466 is restarted	
Clinical findings	
Signs suggestive of clinical TLS (eg, acute kidney injury, cardiac arrhythmia/dysrhythmia ^b , hypotension ^c , heart failure ^c)	
 Initiate supportive therapy as per standard clinical practice Delay AZD0466 for up to 14 days AZD0466 at one lower dose following resolution

Table F29 AZD0466 Dose Modifications for Tumour Lysis Syndrome

Abnormality	Action with AZD0466

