Symptoms suggestive of clinical TLS ^b (eg, oliguria ^d , seizure, nausea, vomiting, muscle cramps ^c , neuromuscular instability ^c)	
 For clinical TLS, initiate supportive therapy and withhold AZD0466 until resolution of symptoms AZD0466 can be withheld up to 14 days Restart AZD0466 at one lower dose Patients should be encouraged to maintain oral hydration

^a Recommended prophylaxis adapted from MD Anderson Cancer Center guidance and Cairo and Bishop 2004.

^b Probably or definitely caused by hyperkalaemia or hypocalcaemia.

^c Probably or definitely caused by hypocalcaemia.

^d Average urine output of < 0.5 mL/kg/h, lasting for > 6 hours.

TLS = tumour lysis syndrome; ULN = upper limit of normal.

F 1.3 Treatment of Tumour Lysis Syndrome

Signs and symptoms of clinical TLS (including but not limited to acute kidney injury, oliguria, nausea, vomiting, seizure, muscle cramps, neuromuscular irritability, cardiac arrhythmia/dysrhythmia, hypotension, or heart failure) should be managed according to standard clinical practice. Additional IV hydration may be administered as clinically indicated in patients with diarrhoea and/or nausea and vomiting.

Recommendations for management of specific laboratory abnormalities is summarised in [Table F30](#).

Table F30 Recommended Management of Electrolyte Abnormalities in Tumour Lysis Syndrome

Abnormality	Management recommendations
Hyperphosphataemia	
Moderate (≥ 2.1 mmol/L)	
 Avoid IV and oral phosphate and limit dietary sources Administer phosphate binder
Severe	Dialysis or haemofiltration may be required
Hypocalcaemia (≤ 1.75 mmol/L)	
Asymptomatic	
 No therapy Patients with acute hypocalcaemia and hyperphosphatemia should not receive calcium repletion until phosphate level has normalised
Symptomatic	
 Calcium gluconate ^a 50 to 100 mg/kg by slow IV infusion with ECG monitoring
Calcium-phosphate product	
≥ 50 mg ² /dL ²	
 Ensure hydration is maintained and alkalinisation is discontinued

Table F30 Recommended Management of Electrolyte Abnormalities in Tumour Lysis Syndrome

Abnormality	Management recommendations
Hyperkalaemia	
Moderate (≥ 6.0 to < 7.0 mmol/L) and asymptomatic	
 Avoid IV and oral potassium ECG monitoring Administer sodium polystyrene sulfonate

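### For a related Grade ≥3 cardiac sign suggestive of clinical TLS, Sections 6.6.6.5 and 10.6.6.3 stop AZD0466 for good while Table F29 resumes it at a lower dose, and no text says which governs

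*Protocol*

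**What the plan says.** **Cardiac rule.** Section 6.6.6.5 first lists findings for which dosing is withheld. Its last bullet is stricter: "AZD0466 should be permanently discontinued if a CTCAE Grade" ≥3 "cardiac AE of any duration occurs during study intervention, if considered by the Investigator to be related to study intervention". Section 10.6.6.3 repeats the stop inside the DLT definition, for a "cardiac AE of any duration occurs at any time during study intervention", again if considered related. Neither place mentions TLS.

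**TLS rule.** The signs row of Table F29 in Appendix F 1.2 opens "Signs suggestive of clinical TLS (eg, acute kidney injury, cardiac arrhythmia/dysrhythmia" and goes on to hypotension and heart failure. Footnote b, attached to the arrhythmia, reads "Probably or definitely caused by hyperkalaemia or hypocalcaemia". Footnote c, attached to heart failure, reads "Probably or definitely caused by hypocalcaemia". The action is supportive therapy, a delay of up to 14 days, then "AZD0466 at one lower dose following resolution". That last line lacks a verb, but the neighbouring symptoms row says restart, so resumption is the natural reading. The row sets no grade limit and does not refer to Section 6.6.6.5.

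**Recording rules.** Under Section 8.3.4, "the recording of diagnoses is preferred (when possible) to recording a list of signs and symptoms". Appendix F 1.4 has TLS reported as laboratory or clinical TLS with its own CTCAE grade.

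**The concern.** A single event can meet both texts. Two sites could then do opposite things after the same related Grade ≥3 arrhythmia: one stops AZD0466 permanently, the other gives it again within about two weeks.

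TLS is an adverse event of special interest and the reason for the intra-patient ramp-up. Cardiovascular toxicity is listed in Table 1 as an important potential risk of the drug in its own right. Footnotes b and c accept an electrolyte cause that is only probable. If that attribution is wrong, the TLS route re-exposes a patient who had direct Grade ≥3 cardiotoxicity, which is the outcome the cardiac stop is there to prevent.

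**Working it through.** No arithmetic applies. The check sets the two instructions side by side and then looks for any text that ranks them.

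| | Sections 6.6.6.5 and 10.6.6.3 | Table F29, signs row |
|---|---|---|
| Event | any cardiac AE | arrhythmia/dysrhythmia or heart failure as a sign suggestive of clinical TLS |
| Grade | CTCAE ≥3 | no limit |
| Causality | related, in the Investigator's view | electrolyte cause probable or definite |
| Action | permanent stop | delay up to 14 days, then one lower dose |
| Exception for the other text | none | none |

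**Can one event meet both causality conditions?** Yes. Appendix F 1 describes TLS as a known effect of antitumour therapy. An Investigator can therefore attribute the arrhythmia to hyperkalaemia and still answer yes to the relatedness question in Section 8.3.3. Footnote a of Table G32, which speaks of events not attributable to the therapeutic agent, belongs to Cairo-Bishop grading and is attached to neither rule.

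**Does the restart sentence closing Section 6.6.6.5 help?** No. It fits the withheld findings. It cannot sensibly undo a permanent stop, and Section 10.6.6.3 repeats the stop without it.

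**Does another text rank the two?**
- Section 6.6.6.3 points to Appendix F for TLS, but does not say that Appendix F overrides Section 6.6.6.5.
- The heading of Table 9 sends cardiac changes to Section 6.6.6.5. It takes them out of Table 9 and is silent on Appendix F.
- Section 6.6.7 refers to the Study Physician only scenarios that are not described. This one is described, with two different actions.
- Section 6.6.6.1 gives the Investigator discretion over dose modification, Section 7.1 stops treatment for any AE that contraindicates further dosing, and Section 8 requires immediate safety concerns to be discussed with the Sponsor. These lower the risk without choosing between the instructions.

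**When is the overlap sharpest?** Table G31 defines clinical TLS as laboratory TLS plus a clinical criterion, and laboratory TLS needs two or more metabolic abnormalities in the same 24 hours. Table F29 asks only for signs suggestive of clinical TLS. A Grade 3 arrhythmia with hyperkalaemia alone can fit the Table F29 row without meeting the definition of clinical TLS. It is then recorded as a cardiac AE, Section 6.6.6.5 applies on its face, and Table F29 still says resume.

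**The case against.** The strongest reply is that the protocol treats cardiac manifestations of TLS as TLS. Section 8.3.4 records signs separately only when they are not generally part of the diagnosis. Table G31 makes arrhythmia and heart failure with the stated electrolyte cause criteria of clinical TLS. Appendix F 1.4 then has the event reported as clinical TLS, and Section 10.6.6.3 takes TLS out of CTCAE grading for DLT purposes. On that route no separate cardiac AE exists to trigger Section 6.6.6.5. Appendix F 1.4 also grades any TLS at CTCAE 3 or above, so Table F29 was evidently written with Grade 3 TLS in mind.

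Much of this stands, and it narrows the point. A reader might infer that the texts contradict each other outright for every confirmed clinical TLS event with a Grade ≥3 cardiac sign. The documents do not support that, because the recording rules give a coherent path through Table F29. But those are rules for recording and DLT grading, and none is stated as a dosing exemption. They also do not reach suggestive signs without confirmed laboratory TLS. The Grade 3 in Appendix F 1.4 is the grade of the TLS, which can accompany a milder cardiac sign, so it does not show that resumption was meant after a Grade ≥3 cardiac event.

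Reading the specific rule over the general one does not settle it either: one text is specific to cardiac events, the other to TLS.

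A reader might also infer a second conflict, between the Table 9 stop for Grade 4 non-haematologic toxicity and Table F29 for non-cardiac TLS. The documents do not support pressing that, since the pointer in Section 6.6.6.3 already favours Table F29 there.

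**Conclusion.** The conflict is real but narrow, and it should be fixed. It covers arrhythmia/dysrhythmia or heart failure that is suggestive of clinical TLS, attributed to hyperkalaemia and/or hypocalcaemia, CTCAE Grade ≥3 and considered related. It is plain when the event is recorded as a cardiac AE, and unresolved when it is absorbed into a TLS diagnosis. Cardiac signs of lower grade, or judged unrelated, do not trigger the permanent stop and raise no conflict.

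Few events are expected. All the conditions must coincide, patients at high TLS risk or with bulky disease (≥10 cm) are excluded, and prophylaxis is required for everyone. The documents give no expected TLS rate, so no count is offered.

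A reader might infer damage to the statistical design. There is none: no hypothesis, sample size or analysis method depends on which text a site follows. An affected patient could at most move in or out of the tabulation of AEs leading to discontinuation.

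The conclusion rests on two assumptions: the verbless line in Table F29 means resumption, and an Investigator may judge a TLS-driven cardiac sign related.

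**What to change.** Add one sentence to the signs row of Table F29: *If a CTCAE Grade ≥3 cardiac event is considered related to study intervention, permanently discontinue AZD0466 (Section 6.6.6.5).*

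This direction is preferred because the stop already appears twice in the protocol body, cardiovascular toxicity is an important potential risk, and a probable electrolyte cause leaves room for misattribution. The clinical cost is that some patients with reversible, electrolyte-driven events lose the option to resume.

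If the sponsor intends those patients to resume, it should instead write an explicit TLS exception into both Section 6.6.6.5 and Section 10.6.6.3. Either way the change is a sentence or two, with no new procedures, visits or patients. Adding Table F29 to the cross-reference in Section 6.6.7 would not be enough, because it would not say which text prevails.

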6.6.6.1 Dose Modifications

AZD0466 may be withheld and the dose reduced due to haematologic or non-haematologic toxicities. In general, no AZD0466 dose modification is required if a patient experiences a Grade 1 or Grade 2 AEs. However, AZD0466 treatment should be modified or discontinued when the AEs described in this section are observed.

AZD0466 dose modification is at the discretion of the Investigator. However, some considerations have been provided.

- For platelet and liver changes, consider Q2W ([Table 6](#)) and at second occurrence, consider triggering dose reductions ([Table 7](#)).
- For AEs other than platelet and liver-related toxicities, consider reducing the dose ([Table 7](#)).
- Dose modifications can be done in two ways, which include dose reduction and frequency change (from weekly to bi-weekly schedule). Frequency changes are not possible during ramp-up. A maximum of 3 dose modifications is acceptable, except for CTCAE Grade 3 or 4 haemorrhage and any intracranial haemorrhage or haematoma, of which only one event is allowed. See [Table 8](#), [Table 9](#), [Table 10](#), and [Table 11](#).

Table 6

Dose Frequency Changes

CCI

[figure not shown]
[figure not shown]

Table 7

Dose Reduction Modifications

CCI

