6.6.6.2 Dose Modifications Based on Haematologic Parameters

If a patient experiences a clinically significant and/or **unacceptable haematologic toxicity** (including a DLT) considered by the Investigator to be related to study intervention and not attributable to the disease (or to disease-related processes) under investigation, dosing in subsequent cycles will be withheld and may subsequently be restarted at one lower dose (equivalent to one dose reduction) and supportive therapy ([Appendix F](#)) administered as

required. Recommended dose modifications for haematologic toxicities associated with AZD0466 observed in patients with haematologic malignancies are shown in [Table 8](#).

Prior to the start of the next treatment cycle, patients must have a recovery of neutrophils $> 1000/\mu\text{L}$ and platelets $> 75\,000/\mu\text{L}$.

Table 8 Recommended Dose Modifications for Haematologic Toxicities

Toxicity grade	Occurrence	Action
Grade 3 or 4 neutropenia	Cycle 1	
 Continue AZD0466 Consider introducing growth factors (eg, G-CSF) after discussion with the Study Physician and continue to monitor ANC If Grade 4 > 7 days, discontinue AZD0466
	Cycle 2 and subsequent cycles	
 Withhold AZD0466 until ANC resolution to $\geq 1.0 \times 10^9/\text{L}$ Consider introducing growth factors (eg, G-CSF) and continue to monitor ANC If resolution occurs in ≤ 14 days, restart AZD0466 at same dose level, after discussion with Study Physician If resolution occurs in > 14 days but ≤ 21 days, restart AZD0466 at one lower dose (Table 7). A maximum of 3 dose reductions is permitted Discontinue AZD0466 if no resolution to ANC $\geq 1.0 \times 10^9/\text{L}$ in < 21 days
Febrile neutropenia/neutropenic infection (any grade lasting > 2 days)	Cycle 1	
 Consider introducing growth factors (eg, G-CSF), evaluate patient for infection, and begin antibiotic treatment per institutional guidelines Withhold AZD0466 until infection is resolved, and antibiotics are no longer required (except prophylactic antibiotics), and ANC $\geq 1.0 \times 10^9/\text{L}$ Restart at current dose after discussion with Study Physician

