	Cycle 2 and subsequent cycles	
 Consider introducing growth factors (eg, G-CSF), evaluate patient for infection, and begin antibiotic treatment per institutional guidelines Withhold AZD0466 up to 21 days until infection is resolved, and antibiotics are no longer required (except prophylactic antibiotics), and ANC $\geq 1.0 \times 10^9/\text{L}$ 
 On first occurrence, restart AZD0466 at one lower dose (Table 7), after discussion with Study Physician On second occurrence, consider restart AZD0466 at one lower dose than the previous dose (Table 7), after discussion with Study Physician On third occurrence, restart AZD0466 at one lower dose than the previous dose (Table 7), after discussion with Study Physician unless there is no clear evidence of clinical benefit, then consider discontinuing AZD0466

Table 8 Recommended Dose Modifications for Haematologic Toxicities

Toxicity grade	Occurrence	Action
CTCAE Grade \geq 3 thrombocytopenia without the presence of significant bleeding	First occurrence	
 Withhold AZD0466 until values return to CTCAE Grade \leq 1 Restart AZD0466 at one lower dose (Table 7) if values resolve to CTCAE Grade \leq 1 within 14 days Discontinue AZD0466 if the above criteria are not met
	Second occurrence	
 Withhold AZD0466 until values return to CTCAE Grade \leq 1 Restart AZD0466 following the Q2W schedule (Table 6) if values resolve to CTCAE Grade \leq 1 within 14 days Discontinue AZD0466 if the above criteria are not met
	Third occurrence	
 Withhold AZD0466 until values return to CTCAE Grade \leq 1 Restart AZD0466 at one lower dose, maintaining the Q2W schedule (Table 6 and Table 7) if values resolve to CTCAE Grade \leq 1 within 14 days, there is clear evidence of clinical benefit and after discussion with Study Physician Discontinue AZD0466 if the above criteria are not met
	Fourth occurrence	
 Discontinue AZD0466
Presence of significant bleeding events with or without thrombocytopenia, such as: 
 Grade 3 or 4 haemorrhage Any intracranial haemorrhage or haematoma 	Any	
 Maintain platelets at $\geq 50 \times 10^9/L$ until resolution of bleeding Discontinue AZD0466

ANC = absolute neutrophil count; G-CSF = granulocyte colony-stimulating factor; Q2W = every 2 weeks.

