Severe (≥ 7.0 mmol/L) or symptomatic	
 As above, plus Calcium gluconate^a 100 to 200 mg/kg by slow IV infusion if concurrent ECG changes (including life-threatening arrhythmias) Regular IV insulin and dextrose, monitor blood glucose closely Consider sodium bicarbonate ^a if patient is acidaemic Consider albuterol (to be avoided in patients with acute coronary disease) Dialysis may be required
Renal dysfunction (uraemia)	
 Fluid and electrolyte management Uric acid and phosphate management Adjust doses of renally excreted medication Dialysis or haemofiltration may be required

^a Sodium bicarbonate and calcium gluconate should not be administered through the same line.

Recommended management adapted from MD Anderson Cancer Center guidance and [Coiffier et al 2008](#).

ECG, electrocardiogram; IV, intravenous.

Laboratory parameters indicating TLS (including blood urea nitrogen, creatinine, phosphate/phosphorus, uric acid, calcium, potassium, and LDH) will be evaluated. Fluid balance must be monitored per institutional standards. If more aggressive hydration management is indicated, patient hospitalisation will be considered at Investigator discretion. Allopurinol prophylaxis should be considered based on institutional guidelines.

F 1.4 Reporting Adverse Events of TLS

The Investigator will report TLS as an adverse event or serious adverse event of “laboratory TLS” or “clinical TLS” according to the classification of TLS in Appendix [G 1](#). For the purposes of adverse event reporting, a CTCAE grade for TLS should also be recorded, as follows:

- CTCAE Grade 3: TLS present
- CTCAE Grade 4: TLS with life-threatening consequences; urgent intervention indicated
- CTCAE Grade 5: Death

Tumour lysis syndrome will also be graded according to Cairo-Bishop criteria for the purposes of dose-limiting toxicity assessment and summary of adverse events of special interest (Appendix [G 2](#); [Cairo and Bishop 2004](#)).

F 2 Guidance for Management of Haematologic Changes

F 2.1 Thrombocytopenia and Haemorrhage

Platelet transfusions are permitted as per institutional standards. However, due to the mechanism of action of AZD0466, platelet transfusion may have limited efficacy within 24 to 48 hours after AZD0466 infusion.

AZD0466 should be withheld in presence of significant bleeding events with or without thrombocytopenia, such as:

- Grade 3 or 4 haemorrhage
- Any grade serious haemorrhage event

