- Any grade intracranial haemorrhage or haematoma

However, if there is evidence that the patient is experiencing clinical benefit with AZD0466, restarting at a reduced dose may be considered following discussion with the Study Physician. AZD0466 should be discontinued if significant bleeding reoccurs.

Anticoagulants and aspirin are not allowed during the study; other anti-aggregants may be used with caution.

F 2.2 Neutropenia and Febrile Neutropenia

The use of G-CSF (eg, filgrastim) or GM-CSF (eg, sargramostim) may be used for management of severe neutropenia or febrile neutropenia, as indicated by the current American Society of Clinical Oncology guideline and according to Investigator's clinical judgement. The use of long-acting pegylated G-CSF (eg, pegfilgrastim) is not permitted during study intervention.

F 2.3 Anaemia

Patients already receiving erythropoietin at screening may continue to receive it during study intervention, provided they have been receiving erythropoietin for > 1 month at the time study intervention is started.

Prophylaxis in Cycle 1: Prophylactic erythropoietin should not be started during Cycle 1.

Prophylaxis in Cycle 2 and beyond: Prophylactic erythropoietin may be started during Cycle 2 or in subsequent cycles.

Use of the long-acting erythropoiesis-stimulating agent, darbepoetin, is not permitted during study intervention.

Blood transfusions may be administered at the discretion of the Investigator.

F 3 References

Cairo and Bishop 2004

Coiffier et al 2008

Coiffier et al 2008. University of Texas MD Anderson Cancer Center 2018 Tumor lysis syndrome (TLS) in adult patients. 2018. Copyright University of Texas MD Anderson Cancer Center 2018.

Howard et al 2011

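### After a Grade 3–4 or intracranial bleed, Table 8 stops AZD0466 at the first event, but Appendix F 2.1 permits a reduced-dose restart

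*Protocol*

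**What the plan says.** **Protocol Section 6.6.6.2, Table 8.** The last row covers significant bleeding, with or without thrombocytopenia, and gives Grade 3–4 haemorrhage and any intracranial haemorrhage or haematoma as examples. It applies at every occurrence. Platelets are to be supported "until resolution of bleeding Discontinue AZD0466" (two bullets that run together in the extracted text). The row has no restart option.

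**Protocol Section 6.6.6.2, text before the table.** The general sentence concerns haematologic toxicity "considered by the Investigator to be related to study intervention and not attributable to the disease (or to disease-related processes) under investigation" and allows a later restart one dose lower. Table 8 is then introduced as "Recommended dose modifications for haematologic toxicities associated with AZD0466 observed in patients with haematologic malignancies".

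**Protocol Section 6.6.6.1.** Up to three dose modifications are acceptable, except for "Grade 3 or 4 haemorrhage and any intracranial haemorrhage or haematoma, of which only one event is allowed". The same bullet refers the reader to Tables 8 to 11.

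**Protocol Appendix F 2.1.** Here "AZD0466 should be withheld in presence of significant bleeding events with or without thrombocytopenia". The examples are Grade 3–4 haemorrhage, serious haemorrhage of any grade, and intracranial haemorrhage or haematoma of any grade. Then "restarting at a reduced dose may be considered following discussion with the Study Physician". That option carries a condition: it is open only "if there is evidence that the patient is experiencing clinical benefit with AZD0466". Last comes the rule for a second bleed: "AZD0466 should be discontinued if significant bleeding reoccurs".

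**Pointers.** Section 6.6.7 sends questions of resumption to Tables 8 to 11. Table 1 (Section 2.3.1) places dose modification in Section 6.6 and toxicity management in Appendix F.

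**The concern.** Both texts are current and start from the same trigger, but they prescribe different actions at the first event. A site that opens Appendix F to manage a bleed finds a complete dosing rule there: hold, restart if conditions are met, stop on recurrence. A site that opens Table 8 finds a stop.

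What is at stake is re-exposure after a severe or intracranial bleed. Section 4.5 describes thrombocytopenia as an on-target effect, and Appendix F 2.1 itself warns that platelet transfusion may work poorly in the 24 to 48 hours after an infusion. Two sites could treat the same patient in opposite ways, each citing the protocol.

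**Working it through.** There is no planned figure to reproduce. The check compares the texts.

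| Question | Table 8 | Appendix F 2.1 |
|---|---|---|
| Grade 3–4 haemorrhage covered? | Yes | Yes |
| Intracranial haemorrhage or haematoma covered? | Yes | Yes |
| Serious haemorrhage of lower grade? | Not named; list is open-ended | Named |
| Action at event 1 | Discontinue | Withhold |
| Restart after event 1 | None | Reduced dose, with clinical benefit and Study Physician discussion |
| Discontinuation at | Event 1 | Recurrence (event 2) |
| Permitted restarts | 0 | 1 |

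**Step 1: is the trigger the same?** Yes, for the two event classes named in both lists. Serious haemorrhage of lower grade appears only in Appendix F. Because Table 8 gives examples rather than a closed list, it cannot be said whether that class falls inside or outside the table, so it is left out of the conflict.

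**Step 2: does Table 8 mean a permanent stop?** The row does not say permanently. But other rows of Table 8 use withholding for temporary stops and state restart conditions; this row does neither. A permanent stop is the natural reading.

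**Step 3: does Section 6.6.6.1 settle it?** Allowing only one event can mean that the first event ends treatment, or that one event is tolerated. The reference to Table 8 in the same bullet favours the first reading, but the clause does not say so.

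**Step 4: is there a precedence rule?** Section 6.6.7 and Table 1 favour Table 8. So does Section 6.6.6.2, whose own reference to Appendix F is for supportive therapy. None states that Table 8 overrides Appendix F. Appendix F also carries dosing rules of its own (F 1.2, for tumour lysis syndrome), so a reader cannot assume it is limited to supportive care.

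**Step 5: which bleeds are affected?** The relatedness condition sits in the general sentence of Section 6.6.6.2. The bleeding row of Table 8 and the exception in Section 6.6.6.1 carry no such condition, and neither does Appendix F 2.1. For bleeds considered related to AZD0466, both rules apply on any reading.

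**Step 6: size.** Permitted restarts: 1 − 0 = 1.

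**The case against.** The best case on the other side is that the protocol already leans clearly towards Table 8: resumption is sent there, dose modification is assigned to Section 6.6, and Section 6.6.6.1 cites the table. Table 8 is also titled as recommended, and Section 6.6.6.1 leaves dose modification to the Investigator's discretion, so neither rule is absolute. A restart under Appendix F needs evidence of benefit and a discussion with the Study Physician. Section 7.1 separately requires permanent discontinuation for any adverse event that the Investigator or sponsor judges to rule out further dosing.

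Most of this is accurate, and it lowers the chance of an inappropriate restart. It does not remove the conflict. Pointers are not a precedence statement. Discretion softens both rules without choosing between them. The Study Physician is a real checkpoint but works from the same two texts.

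Three stronger readings are tempting and not supported:

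- A reader might infer a number of extra infusions from two years of weekly dosing. No valid bound follows. Appendix F 2.1 does not bar a restart within Cycle 1, the synopsis and Section 10.6.6.2 allow responders to continue past two years, and Section 10.6.6.2 covers Part B only.
- A reader might take the reference in Section 6.6.6.3 to Appendix F for specific adverse events as proof that Appendix F governs here. That section concerns non-haematologic toxicity, so it is weak support.
- A reader might infer that the Table 8 stop is confined to drug-related bleeds, or that the conflict is established for every bleed whatever its cause. The text settles neither.

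**Conclusion.** The inconsistency is real and should be corrected. For Grade 3–4 haemorrhage and any intracranial haemorrhage or haematoma, Table 8 permits 0 restarts and Appendix F 2.1 permits 1. As written, a site could follow Appendix F exactly and re-dose a patient for whom Table 8 calls for a stop.

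The conclusion rests on two readings: that discontinuation in Table 8 is permanent, and that the conflict holds at least for bleeds the Investigator considers related to AZD0466. It makes no claim about how often such bleeds would occur or how much extra drug would be given. The weight comes from the severity of the event and the ease of correction. The summary of changes describes discontinuation after a single such event, which suggests that the Table 8 rule is the intended one; the finding does not depend on that.

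**What to change.** 1. **Appendix F 2.1.** For Grade 3–4 haemorrhage and any intracranial haemorrhage or haematoma, replace the hold, restart and recurrence text with: *permanently discontinue AZD0466 at the first event, per Table 8*. Do not add a relatedness exemption or express permission to restart after bleeds judged unrelated; the bleeding row of Table 8 has neither, and adding one would weaken a safety rule. If any restart text is kept, limit it to significant bleeds that are neither Grade 3–4 nor intracranial, such as lower-grade serious haemorrhage, if the sponsor decides that Table 8 does not already cover it.
2. **Section 6.6.6.1.** Replace the clause on how many events are allowed with: *a single such event results in permanent discontinuation (Table 8)*.
3. **Section 6.6.6.2.** To the general sentence allowing a restart one dose lower, add: *except significant bleeding events, see Table 8*.

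The cost is a few sentences in the next amendment. Sample size, endpoints and analyses are unaffected.
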